12.4.4 Covariates

Section 7.4: Efficacy analyses will not include the assigned treatment sequence and period order as covariates. Change from baseline analyses will include the baseline measurement as a continuous covariate.

12.4.5 Primary Efficacy Measure

Section 9.1.3: Descriptive statistics showing the raw values and changes from baseline for the 6MWT will be presented for each scheduled visit by treatment group.

A longitudinal model with change from baseline as the outcome variable, implemented through SAS PROC MIXED, will be used to analyze the data. The model will include all measurements of 6MWT. Baseline average 6MWT will be a covariate. The model will include terms for the interaction between visit number and treatment. The contrast between treatment groups at Week 12 will be calculated from the following model:

[REDACTED]

[REDACTED]

LS means for baseline-adjusted 6MWT for each treatment group, LS means of treatment group differences with their associated p-values, and 95% CIs for both will be summarized and presented.

The primary sensitivity analysis will incorporate control-based multiple imputation, which assumes that patients who stop study medication will adopt the experience in the placebo group,

will be used to account for missing data. An addendum to this protocol, to be written before the data are unblinded, will present the SAS program to be used for the multiple imputation.

Section 9.1.4: Sensitivity analyses will explore the extent to which multiple imputation of Week 12 data influences the interpretation of the outcome.

The following describe the sensitivity analysis approach using multiple imputation of the primary outcomes. The analyses will be structured as follows:

- [REDACTED]
- [REDACTED]
- [REDACTED]
- [REDACTED]

Planned sensitivity analyses will be described in an addendum to this SAP, which will be completed around the Blind Data Review but prior to the breaking of the study blind.

Section 9.2.1: At the conclusion of the study, a *blinded* analysis will be performed to assess the extent of missing primary efficacy endpoint data. The Sponsor has estimated the power of this planned study at various sample sizes and determined that the minimum acceptable power (80% for a 2-tailed $\alpha=0.05$) occurs at approximately 200 subjects (~100 per treatment) providing evaluable primary endpoint data. With a planned sample size of 314 evaluable subjects, if at least 65% of the 6MWD has been collected (or otherwise imputed for death or too ill to walk) across subjects and key visits (Baseline and Week 12), the primary endpoint will remain, as planned, the 6MWD, regardless of actigraphy data.

Section 9.2.3:

The final data resulting will be the combined 6MWD/MVPA ranks data set.

[REDACTED]

Section 9.3.1.3.2: The associations between the observed change from baseline actigraphy measurements of MVPA and overall activity will be contrasted with the magnitude of change for PGA items. Assessments will be made in an exploratory fashion and may include bivariate frequencies and correlations to assess the associations between activity and symptoms measurements made overall and between treatments (as appropriate). A 1-category change on the 5-point PGA scale will be considered clinically meaningful.

Section 9.3.3: The 6MWD and Borg dyspnea composite score is derived based on the results of the 6MWD and the Borg dyspnea scale measuring the degree of dyspnea. The following derivation strategy will be employed to calculate the 6MWD and Borg dyspnea composite score:

[REDACTED]

Descriptive statistics of the raw and change from baseline values for composite score will be presented for each scheduled visit by treatment. The composite score will be treated as a continuous variable. A longitudinal mixed model, similar to that used for the primary analysis of 6MWD, will be used to describe the change from baseline in the composite score over time. A contrast will be calculated for Week 12 to compare the treatment groups with respect to change.

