2.2 PRIMARY ENDPOINT

The primary efficacy endpoint for this study is the change in 6MWD from Baseline to Week 12 in subjects with PH-COPD.

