5 SAMPLE SIZE CONSIDERATIONS

5.1 PLANNED STUDY

The **Original Crossover Design** is a 2x2 crossover study designed to have 90% power to detect a placebo-corrected mean change from baseline difference of 30 meters, assuming that the

standard deviation of differences is 85 meters² and using a 2-group t-test with a 0.01 2-sided significance level, with a sample size of 124 subjects (62 in each sequence group). To account for a discontinuation rate of approximately 10%, the total sample size will be approximately 136 subjects.

The **Contingent Parallel Design** is a parallel-group study designed to use an allocation ratio of 1:1 between inhaled treprostinil and placebo, with a sample size of 266 subjects (133 per treatment) that would provide at least 90% power at a significance level of 0.05 (2-sided hypothesis) to detect a 30 meter between-treatment difference in the change from baseline in 6MWD, assuming a standard deviation of 75 meters. To account for a discontinuation rate of approximately 15%, the total sample size will be approximately 314 subjects. Should there be a switch to the Contingent Parallel Design, the analysis plan described in Appendix 12.4 will be followed.

5.2 [REDACTED]

[REDACTED]

² Note. Due to the smaller sample size expected for the crossover design a more conservative standard deviation of the difference (85 meters) was assumed (compared to 75 meters for a parallel design).

assignment. All safety analyses will be performed on this Safety Population, unless otherwise specified.

A summary table presenting the number and percentages of subjects for each analysis population will be presented by treatment group. Subjects who are excluded from any analysis population will be listed with reason for exclusion. The Sponsor must approve this list before treatment is unblinded and thus before performing final analyses.

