7.4 COVARIATES

Efficacy analyses will include the assigned treatment sequence and period order as covariates. Change from baseline analyses will include the baseline measurement as a continuous covariate.

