9.2 ALTERNATIVE PRIMARY ENDPOINT

At the conclusion of the study, a *fully blinded* analysis will be performed to assess the extent of missing primary efficacy endpoint data (ie, 6MWD data). If the absence of 6MWD data in the Treatment Period, combined across subjects, treatment periods, and key visits (Baseline and Study Week 12) to be used for the final primary endpoint analysis would likely lead to an underpowered study or yield indeterminate results, an alternative primary endpoint will be used for the final primary endpoint analysis.

The alternative primary efficacy endpoint is defined as the ranked value for 6MWD measured at each study visit (if present and otherwise imputed for death or too ill to walk) or the ranked value for MVPA measured corresponding to each study visit (otherwise). These data are termed the combined 6MWD/MVPA ranks data.

[REDACTED]

[REDACTED]

The following sections present the pre-specified procedures to be followed.

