9.2.1 Pre-specified Primary Endpoint Switching Algorithm

At the conclusion of the study, a *blinded* analysis will be performed to assess the extent of missing primary efficacy endpoint data. The Sponsor has estimated the power of this planned study at various sample sizes and determined that the minimum acceptable power (90% for a 2-tailed $\alpha=0.05$) occurs at approximately 88 subjects providing evaluable primary endpoint data. With planned sample size of 136 evaluable subjects, if at least 65% of the 6MWD has been

collected (or otherwise imputed for death or too ill to walk) across subjects, periods, and key visits (Baseline and Week 12), the primary endpoint will remain, as planned, the 6MWD, regardless of actigraphy data.

If the study completes under the Original Crossover Design, the outcome of the analysis will inform a decision to adopt an alternative primary efficacy endpoint of combined 6MWD/MVPA ranks data as follows:

- If data presence $\geq 65\%$ for 6MWD data (Study Weeks 1, 12, 14, and 25), regardless of data presence for actigraphy, the study will use only 6MWD data as the primary efficacy endpoint.
- If data presence $< 65\%$ for 6MWD data (Study Weeks 1, 12, 14, and 25) and the data presence for actigraphy (Study Weeks 1, 12, 14, and 25) is greater than the presence for the 6MWD data, the study will switch and use combined 6MWD/MVPA ranks data as the primary efficacy endpoint.
- In the event that the data presence $< 65\%$ for 6MWD data (Study Weeks 1, 12, 14, and 25) and the data presence for actigraphy (Study Weeks 1, 12, 14, and 25) is equal or lower than the presence for the 6MWD data, the study will use only 6MWD data as the primary efficacy endpoint.

If the study completes under the Contingent Parallel Design, the outcome of the analysis will inform a decision to adopt the alternative primary efficacy endpoint of actigraphy data as follows:

- If data presence $\geq 65\%$ for 6MWD data (Study Weeks 1 and 12), regardless of data presence for actigraphy, the study will use only 6MWD data as the primary efficacy endpoint.
- If data presence $< 65\%$ for 6MWD data (Study Weeks 1 and 12) and the data presence for actigraphy (Study Weeks 1 and 12) is greater than the presence for the 6MWD data, the study will switch and use combined 6MWD/MVPA ranks data as the primary efficacy endpoint.

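### The 65% rule for keeping 6MWD primary is justified in evaluable subjects but worded as a pooled count of 6MWD values, so near-complete baselines can hide a Week 12 shortfall, chiefly in the parallel design

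*SAP*

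**What the plan says.** SAP 2.2 defines the endpoint: "The primary efficacy endpoint for this study is the change in 6MWD from Baseline to Week 12". SAP 9.2 gives the purpose of the switch. If missing 6MWD data "would likely lead to an underpowered study or yield indeterminate results, an alternative primary endpoint will be used".

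For the parallel design, SAP 12.4.5 says that the minimum acceptable power (80%, two-sided alpha 0.05) "occurs at approximately 200 subjects (~100 per treatment) providing evaluable primary endpoint data". It then retains 6MWD "if at least 65% of the 6MWD has been collected (or otherwise imputed for death or too ill to walk) across subjects and key visits", whatever the actigraphy presence. The bullets in SAP 9.2.1 name Study Weeks 1 and 12 as the visits counted.

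For the crossover, SAP 9.2.1 says that the minimum acceptable power (90%, two-sided alpha 0.05) "occurs at approximately 88 subjects providing evaluable primary endpoint data". It continues "With planned sample size of 136 evaluable subjects" and applies 65% across subjects, periods and key visits (Weeks 1, 12, 14 and 25).

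The 136 and 314 that the SAP calls evaluable are the randomized totals after allowance for discontinuation. The figures before that allowance are 124 and 266 (SAP 5.1).

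**The concern.** The justification and the rule use different units. The floors are numbers of subjects who have the endpoint. As worded, the rule counts 6MWD values, and a baseline without a Week 12 value counts towards 65% while contributing no change score.

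The mismatch tends to run one way. Protocol 3.1 requires the randomization visit to be onsite, and Protocol Table 3-2 (footnote e) places the Week 1 6MWT between randomization and first dose, so Week 1 should be nearly complete. Later visits may be by telemedicine, where no 6MWT is done (Protocol 3.3.1.4). Values missing for reasons other than death or being too ill are not imputed (SAP 9.1.2).

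At stake is whether the switch works in the situation it was written for. A large loss of Week 12 walks could leave 6MWD primary below the number of subjects that the SAP gives as its minimum.

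**Working it through.** **Inputs.** Effect 30 m; SD 75 m parallel; SD of differences 85 m crossover (SAP 5.1); two-sided alpha 0.05 (SAP 9.2.1 and 12.4.5); N = 314 and 136. Assumptions of this check: complete Week 1 unless stated, equal arms, noncentral t power.

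**1. The SAP's floors reproduce, and 65% matches them as shares of subjects.**
- Parallel: noncentrality = 30/(2 × 75/√n). At n = 200 this is 30/10.61 = 2.83, power 80.4%. 200/314 = 63.7%.
- Crossover: noncentrality = 30√n/85. At n = 88 this is 3.31, power 90.6%. 88/136 = 64.7%.

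**2. The pooled rule, parallel.** There are 2 × 314 = 628 values; 0.65 × 628 = 408.2, so 409 pass. With 314 baselines, 409 − 314 = 95 Week 12 values are enough.

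| Week 12 values (all paired) | Pooled presence | Power |
|---|---|---|
| 95 | 65.1% | 48.8% |
| 157 | 75.0% | 70.2% |
| 198 | 81.5% | 79.97% |
| 199 | 81.7% | 80.2% |
| 200 | 81.8% | 80.4% |

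With complete baselines, a pooled threshold would have to be about 82%, (314 + 200)/628, to mean 200 pairs. If only 90% of baselines are present (283), 409 − 283 = 126 Week 12 values pass; if all are paired, power is about 61%.

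**3. What Week 6 data could recover, parallel.** For monotone missingness, the effective number at Week 12 is n_eff = 1/[(1 − r²)/n12 + r²/n6], where r is the Week 6/Week 12 correlation of the changes. The documents give neither r nor Week 6 presence; 60% to 90% presence (n6 = 188 to 283) is assumed.
- n12 = 95: r = 0.5, n6 = 188 gives n_eff 108, power 54%. r = 0.8, n6 = 283 gives 165, 72%. At r = 0.9, n6 = 188 gives 71% and n6 = 283 gives n_eff 206, about 81%.
- n12 = 157: r = 0.5, n6 = 188 gives n_eff 164, 72%. r = 0.8, n6 = 283 gives 220, 84%.

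**4. The pooled rule, crossover.** There are 4 × 136 = 544 values; 0.65 × 544 = 353.6, so 354 pass. With Week 1 complete, 354 − 136 = 218 values remain for Weeks 12, 14 and 25. Since 218/3 = 72.7, at most 72 subjects have both changes at that count. Power on 72 complete subjects is 84.0%, against 90.6% at 88. Dropout after a complete Period 1 lowers this to 41 (136 + 136 + 41 + 41 = 354): 59.6% on complete subjects alone. Keeping the 95 Period 1-only subjects in a model with period and sequence gives about 72% (standard error 11.69 m; SD 75 m per period assumed, which with 85 m for differences implies a between-period correlation of 1 − 85²/(2 × 75²) = 0.358).

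**5. The subject-based rule, parallel.** 0.65 × 314 = 204.1, so 205 pairs, power 81.3%.

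**The case against.** **The wording may already mean subjects.** The subject-based floors stand beside the 65%, presence has no stated denominator, and nearby text is redacted (SAP 5.2, parts of 9.2 and 9.2.3). Pooling is the plainer reading, but this limits confidence.

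**The extreme cases are unlikely.** Telemedicine needs Sponsor approval. At the planned 15% loss about 267 pairs remain (0.85 × 314) and pooled presence is about 92%. That stands as to likelihood, but heavy loss of onsite walks is the contingency this rule serves.

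**The floors are not absolute.** Both are approximate, and SAP 9.2.1 expressly keeps 6MWD below 65% when actigraphy presence is no better. This stands. It does not explain why the first test should count unpaired baselines.

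**Adaptation 1 guards the crossover.** The study leaves the crossover if Week 25 presence is below 85% for both 6MWD and actigraphy at about 75% randomized (Protocol 10.2.1). Period 2 dropout removes both measures, so the 41-subject case is partly guarded: with 85% presence at the check, 41 final completers would require at most 48 assessable subjects then (0.85 × 48 = 40.8). The guard is incomplete, because actigraphy alone at 85% lets the crossover continue and losses can follow the check.

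**A reader might infer that a crossover without Week 25 data cannot separate treatment from sequence.** Weeks 1, 12 and 14 alone give 408/544 = 75% and pass, and SAP 7.4 says "Efficacy analyses will include the assigned treatment sequence and period order as covariates". The documents do not support that inference when Week 19 walks exist. Under a model of the form shown for the Borg score (SAP 9.3.2) plus period, Week 19 data make the Week 12 contrast estimable. With Week 19 complete, power is 65%, 78%, 86% and 93% at within-period correlations 0.5, 0.7, 0.8 and 0.9 (SD 75 m and between-period correlation 0.358 assumed). The inference would hold only if Week 19 were also absent, or if the redacted primary model carried sequence-by-visit terms.

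**Conclusion.** The unit mismatch is real on the visible text and matters most in the parallel design. With complete baselines, 95 to 199 Week 12 values of 314 keep 6MWD primary below the SAP's floor of about 200; at 199 the shortfall is nominal, and power without Week 6 information is below 80% up to 198. The loss is large near 95 (49%, or 54% to 72% with Week 6 correlations of 0.5 to 0.8) and may vanish near 157.

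In the crossover the same mismatch lets 72 or fewer subjects with both changes pass at the threshold count when Week 1 is complete, against about 88. That is a weaker point, because Adaptation 1 partly limits it and the mixed model also uses Week 19 and single-period data.

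The result rests on pooling being the operative definition, near-complete Week 1 walks, and the SAP's effect and SDs. For those SDs, SAP 5.1 (footnote 2) states that "a more conservative standard deviation of the difference (85 meters) was assumed (compared to 75 meters for a parallel design"). It does not show that the trial is expected to be underpowered. Confidence is moderate because redacted text may define presence.

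**What to change.** **Parallel (SAP 12.4.5).** Define 6MWD presence as the share of randomized FAS subjects with both Baseline and Week 12 6MWD, counting death and too-ill imputations as present. Keep 65%, which then means 205 of 314.

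**Both designs.** Compute actigraphy presence in the same way as 6MWD presence, since the later bullets compare the two. Describe 136 and 314 as randomized rather than evaluable.

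**Crossover (SAP 9.2.1).** Do not let baselines count on their own towards 65%. Set the criterion from the blinded information the planned mixed model would have (complete and single-period change scores), judged against the stated 90% power. Do not require all four values: with Week 1 complete and independent 85% presence at the other three visits, only 0.85³ = 61% of subjects have all four, so 6MWD would fail the 65% test although mixed-model power is about 93%. State that this departs from the Protocol 10.2.1 wording, which combines subjects, periods and visits; Protocol Section 10 allows such a change in the SAP before database lock.

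**Cost.** Wording only; the check stays blinded and uses data already collected. The combined rank endpoint, whose power is not visible, may be triggered somewhat more often.

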12.4.6 Secondary Efficacy Measures

Section 9.4.1: A longitudinal mixed model will be used to describe the change from baseline for each of the scores over time. A contrast will be calculated for Week 12 to compare the treatment groups with respect to change. The outcome variable will be change from baseline. Independent variables will be treatment, the subject's baseline average SGRQ score, treatment sequence, visit number, and the interaction of visit and treatment.

Section 9.4.2: A longitudinal mixed model will be used to describe the change from baseline in the total score over time. A contrast will be calculated for Week 12 to compare the treatment groups with respect to change. The outcome variable will be change from baseline. Independent variables will be treatment, the subject's baseline average UCSD SOBQ score, treatment sequence, visit number, and the interaction of visit and treatment.

12.4.7 Safety Analyses

Section 10.1: Exposure to treprostinil and placebo will be calculated as the date of last dose minus the date of first dose plus 1. If the date of last dose of study drug was missing or unknown, the return date of study drug will be used as an imputed date. All analyses will be presented by treatment.

Section 10.2: Adverse events are recorded starting from the time each subject signs the ICF until the time a screen failure is documented, study completion, or early termination. All events recorded by the Investigators will be assigned a MedDRA PT and SOC. The most recently available MedDRA version before the database lock date will be used to assign preferred terms and system organ classes. All presentations will present data by treatment received at the time of the event. Non-treatment-emergent AEs observed outside of any study drug exposure will not be presented.

Section 10.5: Descriptive statistics for each clinical laboratory parameter (hematology, serum chemistry, and electrolytes) will be presented by treatment group at baseline, each post-baseline assessment, and End of Study visits for raw data and change from baseline.

Section 10.6: Descriptive statistics for vital signs (heart rate, systolic blood pressure, diastolic blood pressure, respiration rate, weight, BMI) will be presented for both Baseline Visits by treatment. The same statistics will also be presented for each post-baseline assessment and End of Study visits for the raw data and change from the respective baseline. Any clinically significant change from Screening Visit 1 was to be recorded as an AE.

Section 10.7: Descriptive statistics for ECG findings (sinus rhythm [present/absent], heart rate, PR interval, QRS duration, QT interval, interpretation [normal/abnormal]) will be presented by treatment group. Continuous variables will also be presented as the raw values and change from the respective baseline will be presented for each post-baseline assessment by treatment received at the time of the visit. Whenever more than one ECG evaluations are recorded on the same day, the data summaries will use the average of these readings.
